## 3.2 Treatment

### 3.2.1 Randomization Scheme and Treatment Arm Assignment

Subjects will be randomized 1:1 to receive either combination treatment with Liquid Alpha1-PI (Human) plus SMT or placebo plus SMT.

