## 4. GENERAL CONSIDERATIONS FOR DATA ANALYSIS

Unless otherwise specified, continuous variables will be summarized using descriptive statistics

(n, mean, standard deviation, median, minimum, and maximum). Categorical variables will be summarized showing the number and percentage of subjects within each category.

Summary results will be provided for each treatment group. All tabulations will be based on pooled data across centers.

All statistical tests will be two-sided and tested at the 5% level of significance.

Analyses will be performed using SAS for Windows statistical software, version 9.4 or higher (SAS, Cary, NC), except where other software may be deemed more appropriate. In the event that other software is used to perform some analyses, the details will be provided in the Clinical Study Report.

██████████ will perform all efficacy and safety analyses described in this SAP and Grifols will review them.

Subject data will be listed, sorted by treatment group and subject number. When applicable, listings will be additionally sorted by visit and assessment date/time.

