#### **Duration of ICU stay**

The duration (number of days) of ICU stay from Day 1 through Day 29 will be calculated based on ICU admission and discharge dates recorded on the eCRF. Number of days in the ICU will be compared between treatment groups using an ANOVA model, including number of days in the ICU as a dependent variable and treatment group as a fixed effect. From this model, the LS means and 95% CIs for each treatment group, the treatment difference in the LS means, the 95% CI for the difference, and the associated p-value will be presented. If appropriate, an ANCOVA model may instead be used to additionally adjust for baseline characteristics such as age and gender.

In the event the data is highly skewed, e.g. very few subjects with ICU admissions, a sensitivity analysis using a non-parametric Wilcoxon Rank Sum test will be performed. The p-value from Wilcoxon Rank Sum test, as well as the Hodges-Lehmann estimate of the treatment difference and the corresponding 95% CI will be provided.

Subjects who died while in ICU will be assigned as in the ICU for the number of days remaining from the day of death to Day 29 for the analysis. Subjects who were at ICU at study completion will be assigned an ICU end date equals to the date of completion for the purpose of deriving number of ICU days. Subjects who are alive and never admitted into the ICU through Day 29 will be included in the analysis with a value of zero ICU days.

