#### **Duration of mechanical ventilation**

The duration (number of days) on mechanical ventilation from Day 1 through Day 29 will be calculated based on the start/stop dates of mechanical ventilation recorded on the eCRF All Visits

page “General Duration of Hospitalization, & Overall Requirement for Mechanical Ventilation, ICU Admission and/or Oxygen Supplementation”. Number of days on mechanical ventilation will be compared between treatment groups using an ANOVA model, including number of days on mechanical ventilation as a dependent variable and treatment group as a fixed effect. From this model, the LS means and 95% CIs for each treatment group, the treatment difference in the LS means, the 95% CI for the difference, and the associated p-value will be presented. If appropriate, an ANCOVA model may instead be used to additionally adjust for baseline characteristics such as age and gender.

In the event the data is highly skewed, e.g. very few subjects on mechanical ventilation, a sensitivity analysis using a non-parametric Wilcoxon Rank Sum test will be performed. The p-value from Wilcoxon Rank Sum test, as well as the Hodges-Lehmann estimate of the treatment difference and the corresponding 95% CI will be provided.

Subjects who died during the hospitalization without a stop date of mechanical ventilation recorded on the eCRF will be assigned as being on mechanical ventilation for the number of days remaining to Day 29 for the analysis. Subjects who had mechanical ventilation ongoing at study completion will be assigned a mechanical ventilation end date equals to the date of completion for the purpose of deriving duration of mechanical ventilation. Subjects who are never placed on mechanical ventilation through Day 29 will be included in the analysis with a value of zero days on mechanical ventilation.

A listing of all mechanical ventilation and oxygen administration data collected throughout the study will be provided.

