### **Ordinal scales**

- a) The absolute value and change from baseline in the Ordinal scale from Day 1 through Day 29 will be summarized by treatment group and visit using descriptive statistics.

Mean change in Ordinal scales through Day 29 will be evaluated by fitting a linear MMRM similar to the one described above for “assessment of clinical severity.”

- b) The proportion of subjects in each severity category of the 7-point Ordinal scale at Day 15 and Day 29 will be tabulated. The difference in severity category distribution between treatment groups at Day 15 and Day 29 will be examined using proportional-odds cumulative logit model. The cumulative logits model will compare lower ordinal scales to higher ones, or equivalently, less favorable outcomes to more favorable ones. The model may be adjusted for baseline characteristics such as age and gender if appropriate. The estimated odds ratio and 95% CI will be presented. Graphical illustrations of the fitted model will also be presented for Day 15 and Day 29.

The proportional odds assumption will be tested using a score test at the two-sided alpha level of 0.05. If the proportional odds assumption is not satisfied, given the anti-conservative nature of the score test, the proportional odds model will still be used for the analysis, and the results will be presented along with the score test p-value to help put these results in context. If the proportion odds assumption is rejected or if the proportional odds model fails to converge, a sensitivity or alternative analysis using a non-parametric Wilcoxon Rank Sum test will be performed. The p-value from Wilcoxon Rank Sum test, as well as the Hodges-Lehmann estimate of the treatment difference and the corresponding

95% CI will be provided.

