## 9. SAMPLE SIZE AND POWER CALCULATIONS

Because of the urgency and lack of previous prospective COVID-19 data, sample size estimation remains incompletely defined; however, the size of this pilot study is commensurate with other Phase 2 investigations ongoing during the COVID-19 pandemic. Approximately 100 subjects are allowed to be randomized as part of a humanitarian effort against COVID-19.

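### ICU and ventilation days: the Hodges-Lehmann estimate is called for when nearly all values are zero, where it usually reads 0 (0 to 0) even beside a significant Wilcoxon p-value

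*SAP*

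**What the plan says.** SAP Section 6.2 analyses ICU days and mechanical ventilation days by ANOVA, giving LS means, their difference, a 95% CI and a p-value. A rank-based analysis is added under a stated condition. For ICU days: "In the event the data is highly skewed, e.g. very few subjects with ICU admissions, a sensitivity analysis" with the Wilcoxon rank sum test follows. For ventilation days: "In the event the data is highly skewed, e.g. very few subjects on mechanical ventilation, a sensitivity analysis" of the same kind follows. Both give the Wilcoxon p-value "as well as the Hodges-Lehmann estimate of the treatment difference and the corresponding 95% CI will be provided".

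Survivors never admitted to the ICU "will be included in the analysis with a value of zero ICU days", and never-ventilated subjects likewise enter with zero days. Protocol Section 5.2, exclusion 1, keeps out anyone who needs the ICU or invasive ventilation at entry, so zero is possible for every subject. The SAP gives no rule for ties or excess zeros and no other effect measure to accompany the Wilcoxon test.

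For the 7-point scale (*Ordinal scales*), the main analysis at Days 15 and 29 is a proportional-odds model with an odds ratio and CI. Wilcoxon with Hodges-Lehmann (the p-value "as well as the Hodges-Lehmann estimate of the treatment difference and the corresponding" 95% CI) appears only if proportional odds is rejected, when it accompanies the odds ratio, or if the model does not converge, when it takes the model's place.

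**The concern.** The Hodges-Lehmann estimate is the median of all differences between an active and a placebo subject, and its interval comes from order statistics of those differences. It describes a shift of a continuous distribution. When most subjects in both arms have zero days, most differences are exactly zero, and so are the median and both limits. The Wilcoxon test can still be significant, because it weighs negative against positive differences and allows for ties. The table would then show a p-value near 0.01 beside a difference of 0 days with a CI from 0 to 0. That interval states no difference and no uncertainty. A sensitivity analysis meant to help when ANOVA is doubtful would carry no information on effect size in the case it was written for.

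**Working it through.** **Inputs from the documents.** Two-sided 5% tests: "All statistical tests will be two-sided and tested at the 5% level of significance" (SAP Section 4). Size: "Approximately 100 subjects are allowed to be randomized as part of a humanitarian effort against COVID-19" (SAP Section 9). Allocation: "Subjects will be randomized 1:1 to receive either combination treatment" (SAP Section 3.2.1). This gives n = m = 50. The documents state no event rates, category shares or Hodges-Lehmann figure, so there is nothing to reproduce, and all rates below are assumptions.

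**When the interval collapses.** There are 50 × 50 = 2,500 differences. The usual large-sample limits are the C-th smallest and C-th largest, with

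C = floor(nm/2 − 1.96·√(nm(n+m+1)/12)) = floor(1,250 − 1.96·√(2,500·101/12)) = floor(1,250 − 1.96·145.06) = 965.

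The result is therefore exactly 0 (0 to 0) when fewer than 965 differences (38.6%) are negative and fewer than 965 are positive. Only the signs count, so the lengths of stay matter little.

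**Worked example (assumed data).** With non-zero days in 5 of 50 active and 15 of 50 placebo subjects:

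- Differences: 720 negative (28.8%), 202 positive (8.1%), 1,578 zero (63.1%). Neither sign reaches 965, so Hodges-Lehmann is 0 (0 to 0).
- Wilcoxon: the Mann-Whitney count is 720 + 1,578/2 = 1,509, which is 259 above 1,250. With 80 of 100 values tied at zero, the variance factor is 1 − (80³ − 80)/(100³ − 100) = 0.488, and the SD is 145.06·√0.488 = 101.3. Then z = (259 − 0.5)/101.3 = 2.55 and p = 0.011.
- Other measures on the same data: mean difference −3.2 days; Mann-Whitney probability 0.288 + 0.631/2 = 0.60; any use 10% versus 30%, a risk difference of −20 points.

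Putting the tie-adjusted SD into the limits does not help: C rises to floor(1,250 − 1.96·101.3) = 1,051 (42.0%), which makes collapse easier.

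For comparison, 10 of 50 versus 20 of 50 gave 36.8% negative differences, p = 0.021 and still 0 (0 to 0). With 10 versus 22, 39.0% were negative and the CI became −2 to 0.

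**Where it stops.** If a proportion a of active and b of placebo subjects have non-zero days, with similar lengths among users, the expected negative share is b(1 − a) + ab/2 = b(1 − a/2). With a = 10%, this reaches 38.6% at b = 0.386/0.95 = 41%.

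**Simulation**, 2,000 trials per scenario, 50 per arm (for example, gamma-distributed ICU days with mean 10, capped at 29, for 10% vs 24%). Ranges are from repeat runs.

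| Active vs placebo with any days | Expected negative share | CI exactly 0 to 0, among trials with Wilcoxon p < 0.05 |
|---|---|---|
| 2% vs 14% | 13.9% | 100% |
| 5% vs 20% | 19.5% | 99.8% |
| 10% vs 24% | 22.8% | 99% |
| 10% vs 30% | 28.5% | 91–93% |
| 10% vs 35% | 33.3% | 77% |
| 15% vs 40% | 37.0% | 50–53% |
| 20% vs 45% | 40.5% | 22% |
| 30% vs 55% | 46.8% | 1% |

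The point estimate was 0 in at least 97% of significant trials up to 20% vs 40%.

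**The 7-point scale.** Share of significant trials with CI 0 to 0, odds ratios 1.5 to 3:

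- Day 15, subjects spread or mostly severe: 0%, most often an estimate of 1 with a CI of 0 to 1 or 0 to 2.
- Day 29, split between categories 6 and 7: 0–1%.
- Day 29, 60% in category 6: 4–12%.
- Day 29, 65% in category 7: 65–76%.
- Day 29, 80% in category 7: over 99%.

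Non-proportional sets, closer to the SAP's trigger, gave 0%, 23% and 74% with category 7 shares of 30% vs 20%, 80% vs 55% and 85% vs 65% (active vs placebo). At an odds ratio of 0.4 for a worse outcome, the CI included 0 in 88% to 100% of significant trials, depending on the distribution.

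**The case against.** A reader might infer that the same collapse is usual on the 7-point scale. The documents do not support that. The SAP fixes no category distribution, and the interval shrinks to 0 to 0 only when about two thirds or more of subjects share one end category. Otherwise the result is a coarse whole-number shift whose CI usually touches 0, a milder awkwardness. The method is also triggered there only by non-proportional odds or non-convergence.

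A reader might also infer that the report would present proof of no effect. It would not do so alone. These are conditional sensitivity analyses of secondary endpoints in a study without multiplicity adjustment. ANOVA means with a CI stand beside the duration results. For the scale, the odds ratio is kept even if proportional odds is rejected, every category is tabulated and a repeated-measures model is fitted. Only with non-convergence does Hodges-Lehmann lack an odds ratio beside it. Nor should it reach the futility review, since SAP Section 8.2 plans no sensitivity analyses there.

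Two further objections have some weight. All event rates are assumed, and at high rates the problem disappears; but the SAP's own example of the trigger is very few subjects with an event. And ICU admission and ventilation already enter the primary composite and time to clinical progression; but neither isolates any ICU use or any ventilation.

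What remains is that, for the two durations, the prescribed interval is usually degenerate in the situation the SAP names.

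**Conclusion.** The point holds for ICU days and mechanical ventilation days, and it is minor. With few events and 50 per arm, the Hodges-Lehmann result will usually be 0 (0 to 0) even beside a significant Wilcoxon p-value: about 91% to 99% of significant trials at 10% versus 24% to 30%, and about half at 15% versus 40%. This rests on assumed event rates, equal arms of 50 and the usual large-sample limits. The sign-count rule itself is plain arithmetic and does not depend on the simulation. For the 7-point scale only the weaker statement holds: a coarse estimate, of practical importance mainly if the proportional-odds model does not converge.

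**What to change.** In *Duration of ICU stay* and *Duration of mechanical ventilation*, replace the Hodges-Lehmann estimate and CI with the Mann-Whitney probability that an active subject has fewer days than a placebo subject, ties counted half, with a 95% CI that allows for ties. Add the proportion in each arm with any ICU stay or any ventilation, and the risk difference with its CI; the exact unconditional interval in SAP Section 6.1 can serve.

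In *Ordinal scales*, report the same probability with its CI (active subject in the better category, ties counted half) whenever the Wilcoxon test is used, chiefly so that an interpretable effect measure exists if the proportional-odds model does not converge.

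The cost is SAP wording, a few lines of code and one sentence in the report explaining the measure. Design, data collection and the primary analysis are unchanged.

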### **Sustained normalization of temperature**

Sustained normalization of temperature is defined as the temperature  $<36.6$  °C armpit (axillary),  $<37.2$  °C oral, or  $<37.8$  °C rectal sustained for at least 24 hours through Day 29.

- The time to the first occurrence of sustained normalization of temperature will be estimated using the KM method. The KM estimates along with 95% CI, and survival curves will be provided. Based on the KM estimates, the probabilities of achieving first sustained normalization of temperature and associated 95% CIs on Days 15 and 29 will be reported; in addition, the 25th 50th (median), and 75th percentiles of the time to first sustained normalization of temperature with associated 95% CIs will be provided, as data permit. The survival rates between treatment groups will be compared using Log-rank test. The p-value from Log-rank test will be presented.
- The proportion of subjects who have experienced sustained normalization of temperature at any timepoint through Day 29 within each treatment group will be presented along with a two-sided exact (Clopper-Pearson) 95% CI.

The observed difference in the proportion of subjects who achieved sustained normalization of temperature at any timepoint between treatment groups along with the exact unconditional 95% CI for risk difference will be calculated. The null hypothesis of no between-treatment difference will be tested using Chi-square statistic and the p-value will be reported.

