5 SELECTION AND WITHDRAWAL OF SUBJECTS

5.1 Inclusion Criteria

A subject must meet all the following inclusion criteria to be eligible for participation in this study:

GRIFOLS Bioscience Industrial Group	Number	BIG-CL-PPRT-000019	Version	6.0	Status	Effective	Effective Date	08-Dec-2021
	GC2006 -A Multicenter, Randomized, Open-label, Parallel Group Pilot Study to Evaluate the Safety and Efficacy of Prolastin®-CL Liquid plus Standard Medical Treatment (SMT) versus SMT alone in Hospitalized Subjects with COVID-19						Page	43 of 94

1. Hospitalized male or female subject \geq 18 years of age at time of Screening who is being treated for COVID-19. Subjects must be screened within 48 hours (\leq 48 hours) of hospital admission.
2. Has laboratory-confirmed novel coronavirus (SARS-CoV-2) infection as determined by qualitative PCR (reverse transcriptase [RT]-PCR), or other commercial or public health assay approved by regulatory authorities as a diagnostic test for COVID-19 in any specimen during the current hospital admission OR 96 hours prior to the hospital admission date and prior to randomization (the SARS-CoV-2 test results must be performed by a hospital laboratory and the documentation available) .
3. COVID-19 illness (symptoms) of any duration, including **both of** the following:
 - a) Radiographic infiltrates by imaging (chest X-Ray, CT scan, etc.) and/or clinical assessment (evidence of rales/crackles on exam) with SpO₂ $<$ 94% on room air
 - b) **Any One of** the following related to COVID-19: i. Ferritin $>$ 400ng/mL, ii. LDH $>$ 300 U/L, iii. D-Dimers $>$ reference range, or iv. C-reactive protein (CRP) $>$ 40 mg/L
4. Subject provides informed consent prior to initiation of any study procedures.
5. Female subjects of childbearing potential (and males with female partners of childbearing potential) must agree to use of acceptable contraception methods during study (e.g., oral, injectable, or implanted hormonal methods of contraception, placement of an intrauterine device or intrauterine system, condom or occlusive cap with spermicidal foam/gel/film/cream/suppository, male sterilization, or true abstinence*) throughout the study.

*True abstinence: When this is in line with the preferred and usual lifestyle of the subject. (Periodic abstinence [e.g., calendar, ovulation, symptothermal, post-ovulation methods], declaration of abstinence for the duration of a trial, and withdrawal are not acceptable methods of contraception.)

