7.1.2 Secondary Efficacy Variables

The secondary efficacy variables include:

- Assessment of Clinical Severity: Change in NEWS from baseline (Day 1 through Day 29)
The NEWS has demonstrated an ability to discriminate patients at risk of poor outcomes. This score is based on 7 clinical parameters (respiration rate, oxygen saturation, any supplemental oxygen, temperature, systolic blood pressure, heart rate, level of consciousness [Alert, Voice, Pain, Unresponsive]) <https://www.mdcalc.com/national-early-warning-score-news> (Appendix 2)
- Time to clinical response: NEWS ≤ 2 maintained for 24 hours, Day 1 through Day 29
- Time to hospital discharge: defined as duration of hospitalization from Day 1 through Day 29
- If admitted to ICU post randomization: Duration of ICU stay through Day 29
- Duration of any oxygen use Day 1 through Day 29
- If requiring mechanical ventilation post randomization: Duration mechanical ventilation through Day 29
- Absolute value and mean change from baseline in the Ordinal scale Day 1 through Day 29

The Ordinal scale is as follows:

- 1) Death;
- 2) Hospitalized, on invasive mechanical ventilation or extracorporeal membrane oxygenation (ECMO);
- 3) Hospitalized, on non-invasive ventilation or high flow oxygen devices;
- 4) Hospitalized, requiring supplemental oxygen;
- 5) Hospitalized, not requiring supplemental oxygen;
- 6) Not hospitalized, limitation on activities;
- 7) Not hospitalized, no limitations on activities.

- Proportion (percentage) of subjects in each severity category of the 7-point Ordinal scale at Day 15 and Day 29

GRIFOLS Bioscience Industrial Group	Number	BIG-CL-PRT-000019	Version	6.0	Status	Effective	Effective Date	08-Dec-2021
	GC2006 -A Multicenter, Randomized, Open-label, Parallel Group Pilot Study to Evaluate the Safety and Efficacy of Prolastin®-CLiquid plus Standard Medical Treatment (SMT) versus SMT alone in Hospitalized Subjects with						Page	50 of 94

- Time to sustained normalization of temperature and proportion of subjects with normalization of fever at all time points, defined as temperature $< 36.6^{\circ}\text{C}$ armpit, $< 37.2^{\circ}\text{C}$ oral, or $< 37.8^{\circ}\text{C}$ rectal sustained for at least 24 hours
- Number of subjects who develop ARDS through Day 29 ([Appendix 3](#))
- Length of time to clinical progression through Day 29 (defined as the time to death, mechanical ventilation, or ICU admission)

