### 2.2.2 Secondary Efficacy Endpoints

The secondary efficacy endpoints include the following:

- Assessment of Clinical Severity: Change in NEWS from baseline (Day 1 through Day 29).  
The NEWS has demonstrated an ability to discriminate patients at risk of poor outcomes. This score is based on 7 clinical parameters (respiration rate, oxygen saturation, any supplemental oxygen, temperature, systolic blood pressure, heart rate, level of consciousness [Alert, Voice, Pain, Unresponsive]).
- Time to clinical response: NEWS  $\leq 2$  maintained for 24 hours, Day 1 through Day 29
- Time to hospital discharge: defined as duration of hospitalization from Day 1 through Day 29
- If admitted to ICU post randomization: Duration of ICU stay through Day 29
- Duration of any oxygen use Day 1 through Day 29
- If requiring mechanical ventilation post randomization: Duration mechanical ventilation through Day 29
- Absolute value and mean change from baseline in the Ordinal scale Day 1 through Day 29  
The Ordinal scale is as follows:
  - 1) Death;
  - 2) Hospitalized, on invasive mechanical ventilation or extracorporeal membrane oxygenation (ECMO);
  - 3) Hospitalized, on non-invasive ventilation or high flow oxygen devices;
  - 4) Hospitalized, requiring supplemental oxygen;
  - 5) Hospitalized, not requiring supplemental oxygen;
  - 6) Not hospitalized, limitation on activities;
  - 7) Not hospitalized, no limitations on activities.
- Proportion (percentage) of subjects in each severity category of the 7-point Ordinal scale at Day 15 and Day 29
- Time to sustained normalization of temperature and proportion of subjects with normalization of fever at all time points, defined as temperature  $<36.6$  °C armpit,  $<37.2$  °C oral, or  $<37.8$  °C rectal sustained for at least 24 hours
- Number of subjects who develop Acute Respiratory Distress Syndrome (ARDS) through

Day 29

- Length of time to clinical progression through Day 29 (defined as the time to death, mechanical ventilation, or ICU admission)

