#### **4.2 Analysis Populations**

The following three analysis populations will be defined for this study:

The intent-to-treat (ITT) population is defined as all subjects who are randomized. All efficacy analyses will be carried out using the ITT population based on the randomized treatment.

The Per-Protocol (PP) population is defined as the subset of subjects included in the ITT population who do not present major protocol deviations which might have an impact on the primary efficacy endpoint, and complete at least 80% of the IP. The primary efficacy analyses will be carried out using the PP population if different from the ITT population.

The Safety (SAF) population is defined as the subset of subjects who receive at least any amount of Liquid Alpha1-PI (Human) plus SMT or placebo plus SMT. All safety analyses will be carried out using the SAF population based on the treatment actually received rather than randomized treatment.

The validity of a subject for inclusion in each of these populations (ITT, Safety, and PP) will be assessed before unblinding the database and documented in a blinded review report.

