#### 4.6 Data Derivations and Transformations

The following derivations will be used in this study:

Study Day:

- Date of assessment – 1st date of study drug administration + 1 for assessments done on or after the 1st date of study drug administration
- Date of assessment – 1st date of study drug administration for assessments done before the 1st date of study drug administration

Baseline Observation: the last non-missing value prior to the 1st study drug administration.

Duration:

- Duration in days = end date – start date + 1
- Duration in minutes = end time in minutes – start time in minutes

Origin or Start Date for Time to Event Endpoints:

- Time to Clinical Response: date of 1st study drug administration
- Time to Hospital Discharge: date of 1st study drug administration
- Time to Sustained Normalization of Temperature: date of 1st study drug administration
- Time to Clinical Progression: date of 1st study drug administration

Event Date for Time to Clinical Response and time to sustained normalization of temperature:

- If a subject met the criteria for clinical response or sustained normalization of temperature at multiple assessments, the date of the first assessment meeting the definition of clinical response or sustained normalization of temperature will be used as the event date for deriving time to clinical response or sustained normalization of temperature.

Event Date for Time to Clinical Progression

- The event date will be the date of death, the start date of mechanical ventilation, or the date of ICU admission, whichever occurs first.

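### Temperature normalisation is analysed in all randomised subjects, including those already below the threshold before the first dose, which dilutes the log-rank comparison and shrinks the risk difference.

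*SAP*

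**What the plan says.** SAP 6.2 (Sustained normalization of temperature) defines the event as a temperature below a site-specific limit (36.6 °C armpit, 37.2 °C oral, 37.8 °C "rectal sustained for at least 24 hours through Day 29"). A raised temperature beforehand is not part of the definition.

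Two analyses follow.

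- **Time to event.** "The time to the first occurrence of sustained normalization of temperature will be estimated using the KM method", with a log-rank test. Under SAP 4.6 the clock starts at the first study drug administration and "the date of the first assessment meeting the definition of clinical response or sustained normalization of temperature will be used as the event date".
- **Proportion.** Subjects "who have experienced sustained normalization of temperature at any timepoint through Day 29" are compared by a risk difference and a chi-square test.

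On population, SAP 4.2 states: "All efficacy analyses will be carried out using the ITT population based on the randomized treatment". Protocol 5.1, criterion 3, admits "COVID-19 illness (symptoms) of any duration, including" infiltrates and/or rales with SpO2 below 94%, plus one raised laboratory marker. Fever is not required. SAP Table 1 censors subjects who do not normalise or who die, and has no entry for subjects already below the limit.

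The listed endpoint is worded differently. Protocol 7.1.2 has the "proportion of subjects with normalization of fever at all time points", and SAP 2.2.2 repeats it: "Time to sustained normalization of temperature and proportion of subjects with normalization of fever at all time points".

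**The concern.** The endpoint is meant to show how quickly a raised temperature settles. A subject already below the limit before the first dose has nothing to settle. Under the rules above, that subject still supplies an event soon after the clock starts, in whichever arm, and counts as a success in the proportion. Such events add noise to the log-rank statistic and the same block of successes to both arms of the risk difference. A real effect on temperature would be harder to see and would look smaller than it is.

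Separately, a proportion ever normalised over four weeks leaves little room for arms to differ if most survivors get there, and it is not clearly the quantity that the protocol lists.

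The stakes are limited to one of several secondary endpoints. It is, however, among the secondary outcomes listed for the futility look in SAP 8.2.

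**Working it through.** **Inputs from the documents.** About 100 subjects randomised 1:1, so about 50 per arm (SAP 3.1, 9); two-sided 5% tests (SAP 4). The plan states no power, event rate, effect or baseline temperature distribution for this endpoint, so there is no figure of the plan's own to reproduce. Everything else below is assumed. Write f for the share at or above the threshold at the last pre-dose reading.

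**1. Why the log-rank test is diluted.** At an event time with d events among n at risk, n1 of them active, the statistic gains d1 − d·n1/n, with variance d·(n1/n)·(1 − n1/n)·(n − d)/(n − 1). Suppose f = 60% and the 40 subjects already below the limit all have their event first. Their expected contribution to the numerator is 0. Their variance is 40 × 0.25 × 60/99 = 6.1. The 60 who can respond supply at most 60 × 0.25 = 15. So the variance grows by 6.1 or more on 15, and the signal does not grow.

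If those 40 form their own stratum and all have the event at the same time, then d = n. The numerator is n1 − n1 = 0 and the factor (n − d)/(n − 1) is 0, so they drop out.

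**2. Size of the log-rank loss.** Simulation: 50 per arm, daily readings, exponential times, placebo median 4 days, hazard ratio 2.0, subjects already below the limit taken as the earliest events.

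| f | All randomised | At or above threshold only |
|---|---|---|
| 90% | 83% | 88% |
| 75% | 68% | 82% |
| 60% | 51% | 73% |
| 40% | 32% | 56% |
| 30% | 22% | 43% |

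A second set (median 5 days, hazard ratio 1.75) gives 54/30/13% against 67/48/27% for f = 75/50/25%.

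The loss depends on modelling detail. With fixed or random numbers above the threshold and daily or continuous times, f = 60% gave 55–62% in all subjects against 71–74% in the subset. In the same runs the loss was about 5–12 points at f = 75% and 2–3 points at 90%.

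**3. The proportion.** If p is the rate in subjects at or above the threshold, the all-subject rate is 1 − f(1 − p), so the difference between arms is multiplied by f. For 70% vs 90%:

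| f | All-subject rates | Difference | Power, all | Power, subset |
|---|---|---|---|---|
| 100% | 70.0 vs 90.0% | 20 points | 0.71 | 0.71 |
| 75% | 77.5 vs 92.5% | 15 points | 0.56 | 0.58 |
| 50% | 85.0 vs 95.0% | 10 points | 0.38 | 0.42 |
| 25% | 92.5 vs 97.5% | 5 points | 0.21 | 0.23 |

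Restriction regains about 2 to 4 points of power here. With 90% vs 98% it regains under 1 point; with 60% vs 90%, about 3 to 8 points.

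**4. Ceiling.** With exponential resolution over 28 days and no deaths or missing readings, the ever-normalised rate is 1 − 2^(−28/median):

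- median 4 days: 1 − 2^(−7) = 99.2%
- median 8 days: 1 − 2^(−3.5) = 91.2%
- median 10 days: 1 − 2^(−2.8) = 85.6%

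With a control rate of 90% and 50 per arm, power is only 0.51 even if the active arm reaches 99%.

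**The case against.** The strongest reply is that the size of the problem is unknown and may be small. The limits are lower than an ordinary fever cut-off: the NEWS table in Protocol Appendix 2 scores 36.1–38.0 °C as zero, so many subjects normal by NEWS could still sit above 36.6 °C armpit or 37.2 °C oral. At f = 90% the loss is a few points. This stands, and it is why a range is shown; the direction does not change.

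A second reply is that a subset departs from the rule that all efficacy analyses use the ITT population. The subset is fixed by a reading taken before any study drug, so the comparison within it is still randomised. A stratified log-rank test also keeps every subject.

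A reader might infer four stronger points, which the documents do not support.

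- **That subjects already below the limit are events at the first reading.** The definition needs 24 hours, and such a subject can rise above the limit. The SAP does not say whether the pre-dose reading counts or which reading of the run gives the date.
- **That the any-timepoint proportion is near 100%.** No rate is given. Deaths, evaluations required only at Days 15 and 29 for subjects discharged after Day 6, and the worst-case imputation that SAP 4.4 allows when applicable could all lower it.
- **That both tests lose much of their power.** This is true of the log-rank test at low or moderate f, but not of the chi-square test in most of the examples above.
- **That the SAP has dropped the protocol's endpoint.** SAP 2.2.2 keeps the wording, SAP 6.2 gives Kaplan-Meier probabilities at Days 15 and 29, and SAP 7.4 summarises temperature by visit. The phrase about all time points is itself ambiguous. The texts need to be reconciled; the endpoint is not lost.

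**Conclusion.** The point holds as a minor one. The dilution follows from the plan's own rules: no fever requirement at entry, all randomised subjects analysed, an event defined only by being below a limit for 24 hours, and no provision for those already there.

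Under the assumed median of 4 days and hazard ratio of 2.0, the main simulation's log-rank loss runs from about 5 points (f = 90%) to 24 points (f = 40%). It rests on a baseline share that the documents do not give and on how early the uninformative events are dated. For the proportion, the difference shrinks by the factor f, with little change in chi-square power in the 70% vs 90% example. A ceiling is plausible, not established. The mismatch between any timepoint and all time points needs no assumption. The primary analysis is untouched.

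**What to change.** In SAP 6.2:

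1. Analyse time to normalisation and the proportion in subjects at or above the threshold at the last pre-dose reading, using the baseline rule already in SAP 4.6. Alternatively, stratify the log-rank test by that status. Keep the all-randomised analysis as supportive.
2. Report the proportion normalised at scheduled days, so that SAP 6.2 agrees with SAP 2.2.2 and Protocol 7.1.2. Days 5, 15 and 29 are mandatory for everyone.
3. State whether the pre-dose reading can count, which reading of the 24-hour run gives the event date, and how 24 hours is shown after discharge.
4. Apply the same definitions to this endpoint at the futility look.

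The cost is SAP wording, with no new data. The downside is fewer subjects, and so a wider interval if few are above the threshold, for this one secondary endpoint.
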